#### irRC Definitions

#### Best Overall Response and Date of Progression Using irRC (irBOR)

The Investigator will be asked to provide all responses on study and date(s) of progression, if applicable, and the best overall response will be calculated by the Sponsor or designee based on the time point responses and tumor measurements provided by the Investigators.

#### APPENDIX E ADVERSE EVENT MANAGEMENT ALGORITHMS

Management algorithms for the above-mentioned adverse events are provided on the following pages.

### **Endocrinopathy Management Algorithm**

## **GI Adverse Event Management Algorithm**

Rule out non-inflammatory causes. If non-inflammatory cause is identified, treat accordingly and continue I-O therapy. Opiates/narcotics may mask symptoms of perforation. Infliximab should not be used in cases of perforation or sepsis.

## **Hepatic Adverse Event Management Algorithm**

Rule out non-inflammatory causes. If non-inflammatory cause, treat accordingly and continue I-O therapy. Consider imaging for obstruction.

Patients on IV steroids may be switched to an equivalent dose of oral corticosteroids (e.g. prednisone) at start of tapering or earlier, once sustained clinical improvement is observed. Lower bioavailability of oral corticosteroids should be taken into account when switching to the equivalent dose of oral corticosteroids. \*I-O therapy may be delayed rather than discontinued if AST/ALT ≤ 8 x ULN and T.bili ≤ 5 x ULN.

\*\*The recommended starting dose for grade 4 hepatitis is 2 mg/kg/day methylprednisolone IV.

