## 5.6 Criteria to Resume Treatment

Some patients may continue to benefit from treatment, maintaining or improving responses after progression including those treated with steroids.

Restarting applies only to Grade 2 events and some Grade 3 events (skin rash and thyroiditis).

For non-autoimmune or non-inflammatory events, patients may resume treatment with study drug when the drug-related AE(s) resolve to Grade  $\leq 1$  or baseline value, with the following exceptions:

- Patients may resume treatment in the presence of Grade 2 fatigue.
- Evaluation to exclude any additional immune mediated events endocrine, GI, and liver / pancreas function as clinically indicated must be made prior to restarting.
- Non-drug-related toxicity including hepatic, pulmonary toxicity, diarrhea, or colitis, must have resolved to baseline before treatment is resumed.

If the criteria to resume treatment are met, the patient should restart treatment no sooner than the next scheduled time point per protocol. However, if the treatment is delayed past the next scheduled time point per protocol the treatment should resume at the earliest convenient point that is within the 6 week delay period.

If treatment is delayed for > 6 weeks, (> 8 weeks for patients on a steroid taper), the patient must be permanently discontinued from study therapy, except as specified in Section 5.3.

For patients treated with corticosteroids:

- Grade 2 events must resolve to  $\leq$  Grade 1 before considering retreatment.
- Grade ≥ 2 events should have nivolumab held until resolution to ≤ Grade 1 for at least 2 weeks following complete removal from steroid treatment except for maintenance replacement doses for adrenal insufficiency (preferably no greater than 10mg prednisone equivalent daily).
- Grade  $\geq$  3 events should have nivolumab discontinued. Patients with Grade 3 thyroiditis and skin rash may continue therapy as for Grade 2 events with resolution and stable

replacement treatment.

Patients with hepatitis, pancreatitis, pneumonitis, and colitis are at risk for exacerbation with retreatment if there is residual inflammation and should resolve to Grade 0 or baseline before retreatment. Baseline can mean the initial grade *i.e.* Grade <1 where permitted on study.

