#### 6. DOSING DELAYS/DOSE MODIFICATIONS

There will be no dose adjustments allowed. Subjects with infusion delays > 49 days (i.e., 2 missed doses + 7 days) should discontinue the study drugs.

Please refer to Appendix E to the protocol for toxicity management algorithms which include specific treatment guidelines. These algorithms should be followed unless there are specific clinical circumstances which the treating physician indicates variations or alternative treatment is needed.

Generally, we strongly encourage early evaluation, withholding drug, and appropriate treatment as indicated in the management tables and following event specific guidelines.

ALL OTHER	ALL OTHER Management/Next Dose for Nivolumab	
EVENTS*	*Not agent related, or agent related non-immunologically mediated	
$\leq$ Grade 1	No change in dose.	
Grade 2	Hold until $\leq$ Grade 1 OR baseline. Resume at same dose level.	
Grade 3	Hold until $\leq$ Grade 1 continue at investigator discretion.	
Grade 4	Off protocol therapy.	
Recommended management: As clinically indicated.		

ALL OTHER	Management/Next Dose for Nivolumab	
EVENTS**	**Immunologically mediated	
$\leq$ Grade 1	No change in dose.	
Grade 2	Hold until $\leq$ Grade 1 OR baseline. When resolved, resume at same dose level.	
Grade 3	Off protocol therapy (exceptions noted in Section 5.3 )	
Grade 4	Off protocol therapy	
Recommended management: As clinically indicated.		

Skin Rash and Oral Lesions	Management/Next Dose for Nivolumab
$\leq$ Grade 1	No change in dose.*
Grade 2	No change in dose.* May continue on treatment at investigator discretion.
Grade 3	Hold* until $\leq$ Grade 1. Resume at same level at investigator discretion.
Grade 4	Off protocol therapy.

\*Patients with purpuric or bullous lesions must be evaluated for vasculitis, Steven-Johnson syndrome, TEN, and autoimmune bullous disease including oral lesions of bullous pemphigus/pemphagoid. Pruritus may occur with or without skin rash and should be treated symptomatically if there is no associated liver or GI toxicity. Note skin rash typically occurs early and may be followed by additional events particularly during steroids tapering.

Recommended management: See Appendix E for Skin AE management algorithm.

Liver Function AST, ALT, Bilirubin	Management/Next Dose for Nivolumab
$\leq$ Grade 1	No change in dose. May continue on treatment at investigator discretion.

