Grade 2	Hold until UNL or baseline. Resume at same dose level. Consider steroid treatment > 7 days.
Grade 3	Off protocol therapy.
Grade 4	Off protocol therapy.
Continued treatment	nt of active immune mediated hepatitis may exacerbate ongoing inflammation. Holding

drug to evaluate LFT changes and early treatment are recommended.

LFT changes may occur during steroid tapers from other events and may occur together with other GI events including cholecystitis/pancreatitis.

For individuals who are hepatitis B or C positive, viral DNA or RNA load, respectively, should be measured to determine if worsening LFTs are due to immune-mediated hepatitis or infectious hepatitis. Recommended management: See Appendix E for Hepatic AE management algorithm.

Diarrhea/ Colitis	Management/Next Dose for Nivolumab
$\leq$ Grade 1	Hold until Grade 0 or baseline. When resolved, resume at same dose level.
Grade 2	Hold until Grade 0 or baseline. Consider steroid treatment > 7 days.
Grade 3	Off protocol therapy.
Grade 4	Off protocol therapy.
Patients with Grade 2 symptoms but normal colonoscopy and biopsies may be retreated after resolution.	
Patients who require steroids should be taken off study treatment.	
Please evaluate pituitary function prior to starting steroids if possible without compromising acute care.	
Evaluation for all patients for additional causes includes C. diff, acute and self-limited infectious and food	
borne illness, ischemic bowel, diverticulitis, and IBD.	

Recommended management: See Appendix E for GI AE management algorithm for management of symptomatic colitis.

Pancreatitis Amylase/Lipase	Management/Next Dose for Nivolumab
$\leq$ Grade 1	If asymptomatic without evidence of pancreatitis, liver or gallbladder disease, or new onset diabetes, may continue on treatment at investigator discretion.
Grade 2	If asymptomatic without evidence of pancreatitis, liver or gallbladder disease, or new

Pancreatitis Amylase/Lipase	Management/Next Dose for Nivolumab
	onset diabetes, may continue on treatment at investigator discretion.
Grade 3	If symptomatic, hold until Grade 0. If asymptomatic, without clinical, radiographic, or ultrasound evidence of pancreatitis, and no evidence of associated liver or gall bladder disease or new onset diabetes, may continue on treatment at investigator's discretion. Patients who develop symptomatic pancreatitis or DM should be taken off protocol therapy.

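### The Section 6 liver table stops therapy at Grade 3 and 4 without exception, the Appendix E hepatic footnote permits delay up to stated ULN multiples, and no text says which controls

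*Combined protocol and SAP*

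**What the plan says.** Section 6 has its own table for "Liver Function AST, ALT, Bilirubin". At Grade 2 it reads "Hold until UNL or baseline. Resume at same dose level". At Grade 3, and again at Grade 4, it reads "Off protocol therapy". Neither of those rows carries a ULN threshold or an option to delay.

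Section 5.6 agrees with that table: "Restarting applies only to Grade 2 events and some Grade 3 events (skin rash and thyroiditis". Section 5.3 lists the toxicities that may be restarted after high-dose corticosteroids: skin lesions, pruritus, thyroiditis and seventh-nerve palsy. Liver events are not among them.

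The Appendix E hepatic algorithm has a footnote: "I-O therapy may be delayed rather than discontinued if AST/ALT ≤ 8 x ULN and T.bili ≤ 5 x ULN".

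Section 6 brings Appendix E into the protocol: "These algorithms should be followed unless there are specific clinical circumstances which the treating physician indicates variations or alternative treatment is needed". The notes under the liver table also send the reader to Appendix E "for Hepatic AE management algorithm". Section 5.3 refers to both Section 6 and Appendix E when it defines unacceptable adverse events. No section ranks one above the other.

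**The concern.** Both texts decide whether a patient with a raised AST, ALT or bilirubin stays on nivolumab. One stops treatment outright. The other lets it be postponed instead, provided the values stay under two limits. A physician who delays can cite Appendix E, and one who discontinues can cite Section 6.

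This matters to the analysis because discontinuation for intolerable toxicity is a measured outcome. Section 13.1 makes the number of such patients part of the primary safety and tolerability assessment. Section 13.3 uses the same proportion, θ, in the Bayesian monitoring rule. Enrollment stops at 3 discontinuations in the first 12 patients, 4 in the first 19, or 5 before the last patient is enrolled. If the same liver event is a discontinuation at one site and a delay at another, θ partly reflects which page the site followed.

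**Working it through.** The plan gives no figure to reproduce. The check compares the texts and then asks over what range they overlap.

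**Step 1. The texts side by side, for a Grade 3 liver event**

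| Place | Instruction | Liver exception? |
|---|---|---|
| Section 6, liver table | Stop | None |
| Section 5.6 | Grade 3 restart for skin rash and thyroiditis only | None |
| Section 5.3, steroid exceptions | Skin, pruritus, thyroiditis, seventh nerve | None |
| Appendix E, hepatic footnote | Delay permitted in place of stopping | Yes, if AST/ALT ≤ 8 x ULN and total bilirubin ≤ 5 x ULN |

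Elsewhere Section 6 writes exceptions into its tables. Grade 3 skin rash may resume, and the general immune-mediated table refers to the Section 5.3 exceptions at Grade 3. The Grade 3 and 4 liver rows have no such wording.

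**Step 2. Where the footnote applies**

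The footnote presupposes a discontinuation that it softens. Within the liver table, only Grades 3 and 4 discontinue. The flow chart is not shown, so the grade box it is attached to cannot be seen.

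**Step 3. The overlap**

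Let A be AST or ALT and B total bilirubin, both in multiples of ULN. Let a and b be the values above which Grade 3 begins. Section 7.2 adopts CTCAE v4.0 but does not print a or b, so they are assumptions here.

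- The liver table stops a Grade 3 patient if A > a or B > b.
- The footnote permits delay if A ≤ 8 and B ≤ 5.
- Both apply when (a < A ≤ 8 and B ≤ 5) or (b < B ≤ 5 and A ≤ 8).

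This region is non-empty whenever a < 8 or b < 5:

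| Assumed start of Grade 3 | AST/ALT overlap | Bilirubin overlap |
|---|---|---|
| a = 5, b = 3 | above 5 to 8 x ULN, with B ≤ 5 | above 3 to 5 x ULN, with A ≤ 8 |
| a ≥ 8, b = 3 | none | above 3 to 5 x ULN, with A ≤ 8 |
| a = 5, b ≥ 5 | above 5 to 8 x ULN, with B ≤ 5 | none |
| a ≥ 8, b ≥ 5 | none | none |

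In the last row the footnote would have no liver-table discontinuation to modify.

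If Grade 3 is further assumed to run to 20 x ULN for AST/ALT and 10 x ULN for bilirubin, a Grade 4 value exceeds the footnote's limit (20 > 8 and 10 > 5). The overlap is then the lower part of Grade 3 only.

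**Step 4. What one patient is worth**

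One patient is 1/20 = 5 percentage points of the planned sample. A count one short of the first printed boundary is 2/12 = 16.7%; one more makes 3/12 = 25.0% and stops enrollment. The documents do not say how often a liver event would fall in the overlap, so no probability can be attached.

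**The case against.** The best defence is a division of labour. The liver table's column concerns the next nivolumab dose, whereas its pointer to Appendix E is labelled as recommended management. Section 6 describes the algorithms as treatment guidance and lets the physician vary them. Sections 5.3, 5.6 and 6 agree on liver events, while the footnote is generic wording about I-O therapy. On this reading Section 6 governs dosing and Appendix E governs care of the toxicity.

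That supports an inference about intent, but it does not remove the conflict. The footnote itself addresses whether dosing is delayed or stopped. The clause on clinical circumstances allows departure from Appendix E; it does not say that the Section 6 table prevails.

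Several other objections stand and limit the point:

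- A reader might infer two opposite orders. The footnote is permissive, so a site that discontinues complies with both texts. The conflict is between a permission to delay and an unconditional stop.
- A reader might infer that Appendix E re-treats patients with marked liver toxicity. No restart term is visible there. Section 5.6 addresses restart, lists no Grade 3 liver event, and requires hepatitis to return to Grade 0 or baseline before retreatment.
- A reader might infer that the footnote can reach only patients whom the liver table removes. The protocol also stops lower-grade events by other routes: high-dose steroids (5.3), new or worsening immune events during steroids (5.6), delays beyond 6 or 8 weeks (5.3, 5.6, 6), and more than two delays for one event (6). The unseen chart could attach the footnote to such a branch; it would then need reconciling with those rules.
- A reader might see a special hazard in admitting patients with hepatitis B or C at AST/ALT up to 2.5 x ULN. Section 3.1 sets that AST/ALT limit for every patient.

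**Conclusion.** The inconsistency is real and lies in the current text. Section 6, with 5.3 and 5.6, gives Grade 3 liver events no route to delay; the Appendix E footnote gives one within stated limits; and no precedence is stated.

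Its reach depends on two things the documents do not show: the flow-chart box bearing the footnote and the CTCAE cut-points. The collision requires Grade 3 to begin below 8 x ULN for AST/ALT or below 5 x ULN for bilirubin. Under the assumed bands it does not extend to Grade 4.

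The consequence is that compliant sites may classify the same event differently in the toxicity-discontinuation measure and the stopping rule. A reader might infer that the stopping rule is therefore compromised. That goes too far: one reclassified patient changes a stopping decision only when the count is already one short of a boundary, as any single ambiguous event would. The point warrants correction because the boundaries are small counts and the repair is cheap.

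**What to change.** The clinical team should reconcile the Section 6 liver rows, Section 5.3, Section 5.6 and the Appendix E hepatic footnote so that they give one instruction for the same liver values. Which instruction applies is a clinical decision, and none is proposed here. Section 6 should also gain one sentence stating which text controls when an Appendix E algorithm and a Section 6 table differ.

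The cost is a short text edit in those places plus the precedence sentence. The sample size, stopping boundaries and planned analyses need not change. Discontinuation for liver toxicity would then be counted on the same basis at every site.

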## **Neurological Adverse Event Management Algorithm**

Rule out non-inflammatory causes. If non-inflammatory cause, treat accordingly and continue I-O therapy.

## **Pulmonary Adverse Event Management Algorithm**

Rule out non-inflammatory causes. If non-inflammatory cause, treat accordingly and continue I-O therapy. Evaluate with imaging and pulmonary consultation.

## **Renal Adverse Event Management Algorithm**

Rule out non-inflammatory causes. If non-inflammatory cause, treat accordingly and continue I-O therapy

## **Skin Adverse Event Management Algorithm**

Rule out non-inflammatory causes. If non-inflammatory cause, treat accordingly and continue I-O therapy.

#### APPENDIX F PBMC SHIPMENT LOG

### Duke-UNC-Washington University (DUNCWU)

An Early Therapeutics Clinical Trials Network (ETCTN) Partnership

### NCI9925 PBMC Shipment Log

Site Name: \_\_\_\_\_

Date of Shipment: \_\_\_\_\_ FedEx \_ UPS \_

Shipment Tracking Number: \_\_\_\_

Insert copy of this log with shipment and email to [contact].

. . . . . . . . . . .

Subject ID#	Collection Date (mm/dd/yyyy)	Study Visit (Baseline, Cycle# Day#, or End of Treatment)	Tube Type (sodium heparin or ACD)	Number of Tubes/Cryovials

Page \_\_ of \_\_

#### **APPENDIX G TISSUE SHIPMENT LOG**

# **Duke-UNC-Washington University (DUNCWU)** An Early Therapeutics Clinical Trials Network (ETCTN) Partnership

### NCI9925 Tissue Shipment Log

Site Name:

Date of Shipment: \_\_\_\_\_ Fe

Shipment Tracking Number:

Insert copy of this log with shipment and email to [contact].

Subject ID#	Tissue Specimen Date (mm/dd/yyyy)	Study Visit (Baseline or End of Treatment)	Sample Type (block, core, or slides)	Corresponding Accession Number

#### APPENDIX H BIOMARKER SHIPMENT LOG

### Duke-UNC-Washington University (DUNCWU)

An Early Therapeutics Clinical Trials Network (ETCTN) Partnership

### NCI9925 Biomarker Shipment Log

Site Name:

Date of Shipment: \_\_\_\_\_ FedEx [] UPS []

Shipment Tracking Number: \_\_\_\_\_

Insert copy of this log with shipment and email to [contact].

Subject ID#	Collection Date (mm/dd/yyyy)	Study Visit (Baseline, Cycle# Day#, or End of Treatment)	Sample Type (plasma or whole blood)	Number of Tube/Cryovials

#### **APPENDIX I – NEUROLOGICAL EXAMINATION**

Are there mental status defects? (yes or no) If yes, elaborate

Are there cranial nerve defects? (yes or no) If yes, elaborate

Sensory Exam (elaborate for pos answers)

Are there symptoms of tingling, pins and needles, or burning in the extremities? (yes or no) Is examination of vibratory sense impaired? (yes or no) Is examination of proprioception impaired? (yes or no)

Motor Exam

Is there a complaint on of lower extremity weakness? (yes or no) Rate strength on exam as follows (for left and right side):

- 0 = no contraction
- 1 = visible muscle twitch but no movement of the joint
- 2 = weak contraction insufficient to overcome gravity
- 3 = weak contraction able to overcome gravity but no additional resistance
- 4 = weak contraction able to overcome some resistance but not full resistance
- 5 = normal; able to overcome full resistance

Strength of foot flexors: Strength of foot extensors: Strength of lower leg flexors: Strength of lower leg extensors: Strength of upper leg flexors: Strength of upper leg extensors:

Deep tendon reflexes (for left and right side), graded as follows:

- 0 = absent
- 1 = reduced (hypoactive)
- 2 = normal
- 3 = increased (hyperactive)
- 4 = clonus

Ankle jerk: Knee jerk: Biceps: Triceps:

Is there a disturbance of bladder function? (yes or no)

